#### **7.4.7 Medical and Surgical History**

Information on clinically significant previous and concomitant illnesses, or any clinically significant signs or symptoms that are present before informed consent, or pre-existing conditions identified through findings from assessments and examinations done during the Screening Visit will be recorded as medical and surgical history at Screening. For planned procedures/hospitalisations during the trial, documentation should be completed at the time of the Screening.

#### **7.4.8 Physical Exam**

A limited physical examination will be performed at screening.

Assessments for the physical examination should include those systems affected by the SARS-CoV-2 infection. These can include: General appearance, Eyes, Ears/Nose/Throat, Respiratory (Chest/Pulmonary), Heart, Abdomen, Vascular, Neurological, Musculoskeletal, Lymphatic (Lymph nodes), Skin.

Standard of care measurements can be used if they fall within the protocol specific windows.

If during routine clinical care during the study the physician notes any physical findings of interest these should be noted in the eCRF.

#### **7.4.9 Prior and Concomitant Therapies**

All medications (prescription and non-prescription), treatments, and therapies taken by the patient from screening throughout their entire participation in the study, including those initiated prior to the start of the study, must be recorded on the patient's source document and on the appropriate page of the eCRF. The dose, unit, frequency, route, indication, date the medication was started, and date the medication was stopped (if not ongoing) must be recorded.

All Investigational COVID-19 therapeutic agents used both prior to, and current to randomization and participation in the study should be captured in the CRF.

#### **7.4.10 Lung Function Test**

Lung function will be assessed by PaO2 and PaO2/FiO2 ratio analyses, and two patient questionnaires. These assessments should be completed following the time points specified in the schedule of events (See [Table 3](#) and [Section 7.3](#)). Standard of care measurements can be used for PaO2 and PaO2/FiO2 ratio analyses if they fall within the protocol specific windows.

##### **7.4.10.1 PaO2 and PaO2/FiO2 Measurement Considerations**

It is recognized that the performing of PaO2 and PaO2/FiO2 measurements can cause significant discomfort to patients. All efforts should be made in obtaining each PaO2 sample as per protocol. However, if not possible (e.g. patient refuses) at a minimum complete PaO2 measurements at baseline, Days 3, 5, 8, 11, 15 and 29.

For those days where PaO2 measurements are not able to be taken, SpO2 should be obtained. First preference is for these measurements to be taken using a forehead sensor. Fingertip probes may be used if forehead sensors are not available. The site should remain consistent with the

method of testing for the patient over the course of the study, e.g. all SpO2 measurements are taken with only forehead sensors.

#### **7.4.10.1 Extent of Dyspnea (Likert scale)**

The patient should grade his current breathing compared to when he first started the study (from -3 to 3). "0" = no change, "1" =minimally better, "2" =moderately better, "3" =markedly better, "-1" =minimally worse, "-2" =moderately worse, "-3" =markedly worse

For the first questionnaire (at baseline), the patient compares their current shortness of breath to their shortness of breath when they are well.

A copy of the Extent of Dyspnea (Likert Scale) can be found in [Appendix 16.2](#).

#### **7.4.10.2 VAS Questionnaire**

Cough severity will be measured using a 0-100mm Visual Analog Scale (VAS) from “no cough” to “worst cough ever.”

A copy of the VAS Questionnaire can be found in [Appendix 16.3](#).

Note: the site should hand out the Visual Analogue Scale (VAS) to the subject for completion. If this is not possible, any alternative administration of the VAS must be documented clearly in the source. Reasons for an alternative method may include e.g. site policy to avoid document contamination, or a visually impaired subject. The following alternative options are accepted:

- Subject pointing to the VAS with some device and another person adding the line for them.
- If this is not possible, the subject can rank the score 0 – 100 (as the VAS line is 100mm). Site should hold up the VAS in front of the subject and/or describing this to try and retain some visual aspect.

#### **7.4.11 Prohibited Therapy**

Patient should not be taking droxidopa. Single use of ketamine is permitted. Use of unapproved/off label medications for COVID-19 treatment is permitted if they fall under the established local standard of care.

#### **7.4.12 Safety Evaluations**

Adverse events reporting, including clinically significant laboratory abnormalities, physical examinations and vital signs. AE event collection will be performed from signing of ICF, until end of study.

#### **7.4.13 SARS-CoV-2 RNA Testing**

Confirmation of SARS-CoV-2 RNA using one of the methods outlined in the Inclusion criteria should be performed at baseline, Day 5 (or at discharge if sooner), and at Day 15. Additional testing should be done at Day 29 if the patient still has detectable viral RNA at Day 15.

If possible, testing should be done using both qualitative (e.g. positive/negative) and quantitative (e.g. viral RNA load) methods, but at a minimum qualitative testing should be used. The route of testing (nasopharyngeal, oropharyngeal, blood, etc.) should be captured in the CRF.

## **8. ADVERSE EVENTS**

### **8.1 Adverse Event Definition**

An AE is any untoward medical occurrence in a patient or clinical investigation subject, temporally associated with the use of a medicinal product, whether or not considered related to the medicinal product.

Events MEETING the definition of an AE include the following:

- Exacerbation of a chronic or intermittent pre-existing condition including an increase in frequency and/or intensity of the condition
- Any abnormal laboratory test results (urinalysis, haematology, or clinical chemistry) or other safety assessments (e.g. ECGs, vital signs measurements), including those that worsen from baseline, and are felt to be clinically significant in the medical and scientific judgement of the investigator
- Signs, symptoms, or the clinical sequelae of a suspected interaction
- Accidental injuries, reasons for any change in medication (drug and/or dose), reasons for any medical, nursing or pharmacy consultation, or reasons for admission to hospital or surgical procedures
- Overdoses and medication errors of the IP or concomitant medication with and without clinical consequences

Events NOT meeting the definition of an AE include the following:

- The disease being studied or expected progression, signs, or symptoms of the disease being studied, unless judged by the investigator to be more severe than expected for the patient's condition
- Any clinically significant abnormal laboratory findings or other abnormal safety assessments which are associated with the underlying disease, unless more severe than expected for the patient's condition
- Anticipated day-to-day fluctuations of pre-existing disease(s) or condition(s) present or detected at the start of the study that do not worsen

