## 2. INTRODUCTION

### 2.1 Background

COVID-19 is a severe respiratory infection caused by the SARS-CoV-2 virus. The disease occurs was first detected in China's Wuhan province in 2019 and spread globally over several months, in spite of efforts to quarantine infected patients. The disease is characterized by fever, dry cough, and fatigue. A minority of patients have symptoms such as nasal congestion, nasal discharge, sore throat, muscle pain, and diarrhea. Severe patients often suffer from dyspnea and/or hypoxemia one week after symptom onset, and severe patients can rapidly progress to acute respiratory distress syndrome, septic shock, difficult to correct metabolic acidosis, coagulation dysfunction and multiple organ failure. Most patients have a good prognosis and a minority are in critical condition; however, the prognosis of the elderly and those with chronic underlying diseases is more poor ([Novel Coronavirus Pneumonia Diagnosis and Treatment Plan](#)).

[figure not shown]
The mortality rate of the disease has yet to be determined but is generally estimated at <5%. An early published study showed that fatalities are often attributed to respiratory failure, and there is evidence that suggests that COVID-19 mortality might be due to a virus-activated "cytokine storm syndrome" ([Ruan et. al., 2020](#)).

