#### **4.4 Design Justification**

This study represents one of the first repurposed investigations of Ifenprodil in patients with COVID-19 disease. This study will provide information on the safety and clinical efficacy in the SARS-CoV-2 infected population prior to advancing to larger clinical trials, as well as provide critical information for the design of future studies in this population.

The purpose of this study is to determine whether Ifenprodil is effective and safe in the treatment of patients with COVID-19 disease. The primary measure of efficacy will be patient clinical status (on a 7-point ordinal scale) at day 15 in IP versus control group patients. This protocol is based on the recommendations of the [WHO R&D Blueprint Clinical Trials Expert Group](#).

The Phase 2b stage will be an open label study with patients, investigator, site and CRO staff aware of treatment received. The Phase 3 stage of the protocol will also include a placebo arm to allow for double-blinding.

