### **8.4 Adverse Events of Special Interest**

Adverse events of special interest include known side effects of Ifenprodil. Nausea, dry mouth, loss of appetite, heartburn, diarrhea, constipation, headache, dizziness, allergic reactions, and heart palpitations are known to occur in between 0.1 – 5% of patients. Elevated ALT/AST levels have been observed in <1% of patients.

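### In open-label Phase 2b, the disease exemption in Protocol 8.1 lets an investigator who knows the arm decide whether diarrhea enters the adverse event record

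*Protocol*

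**What the plan says.** Protocol 8.1 first defines an adverse event (AE) broadly, as an untoward occurrence whether or not it is thought related to the product. It then gives a list of what does not count. The first item is "The disease being studied or expected progression, signs, or symptoms of the disease being studied, unless judged by the investigator to be more severe"; the yardstick is what would be anticipated given how ill the patient is.

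Protocol 4.4 states who makes that judgement, and with what knowledge: "The Phase 2b stage will be an open label study with patients, investigator, site and CRO staff aware of treatment received". Double-blinding is planned only for Phase 3.

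Two other sections bear on the same symptom:

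- Protocol 2.1, on the disease: "A minority of patients have symptoms such as nasal congestion, nasal discharge, sore throat, muscle pain, and diarrhea".
- Protocol 8.4, on the drug: "Adverse events of special interest include known side effects of Ifenprodil". It continues: "Nausea, dry mouth, loss of appetite, heartburn, diarrhea, constipation, headache, dizziness, allergic reactions, and heart palpitations are known to occur" in 0.1 to 5% of patients.

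Section 8.4 lists these events and their frequencies and gives no recording instruction. SAP 12.2 plans tables of treatment-emergent AEs by system organ class, preferred term and arm. Safety compared with standard of care (SOC) is part of the primary objective (Protocol 3.1).

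**The concern.** An exemption for expected disease signs is common in trials of acutely ill patients, because it keeps the AE record from filling with the disease itself. It is harmless to a between-arm comparison if it works in the same way in every arm. Here there are two reasons why it might not. The person applying it knows the arm, and at least one symptom has two candidate explanations that the protocol itself supplies.

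The same loose stools can be left out on SOC as expected COVID-19 and entered on ifenprodil as a known side effect. The opposite is also possible: on drug they may be put down to the disease. Either way, a causal judgement is made before the event is recorded, although the protocol has a causality field for that purpose. At stake is the comparability across arms of the AE table for an event that the protocol has itself singled out.

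**Working it through.** The plan states no figure on this point to reproduce. The check is mainly a comparison of texts, followed by arithmetic for scale.

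**1. Does the exemption reach diarrhea?** Section 8.1 does not name it. Section 2.1 does, as a symptom of the disease, so an investigator may treat ordinary diarrhea as an expected symptom. It is the only symptom that appears by name both in the 2.1 symptom list and in the 8.4 list.

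**2. Is there an override?** Section 8.4 has none. Section 8.2 describes how events are elicited and recorded but does not address the 8.1 exclusion. SAP 12 analyses what was recorded. So 8.1 decides.

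**3. Is the event captured elsewhere?** Table 3 schedules no measurement of diarrhea. What exists:

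- AEs are enquired about on each hospital day (7.3.2) and on Days 15, 29 and 60 (Table 3), with a standard non-leading question at each visit (8.2.1). This elicits the symptom, but 8.1 then decides whether it is entered.
- All medications are recorded with indication (7.4.9) and tabulated by therapeutic class and arm (SAP 9). Treated diarrhea can show there. The SAP groups purpose as adverse events, medical history or other, so a drug given for an exempted symptom may have no AE to link to.
- Section 8.1 also counts as AEs the reasons for a medication change or for a medical, nursing or pharmacy consultation. That would bring in some cases, unless the disease exclusion is read as an exception to it.

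Untreated diarrhea that prompts no consultation therefore depends on the investigator's decision alone.

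**4. Direction and size.** Let the true rate be d in both arms, and let the share of cases entered be a on drug and b on SOC. The recorded difference is then d × (a − b). Its sign is the sign of a − b, and it cannot exceed d. The documents give none of the three quantities: 2.1 says only that a minority of patients have such symptoms, and 8.4 gives drug side-effect rates.

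**5. Scale.** Inputs: 50 patients per arm (Protocol 4.1, 10.3) and 0.1 to 5% per symptom (8.4).

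- Expected drug-related cases per arm: 0.001 × 50 = 0.05 to 0.05 × 50 = 2.5.
- One entry made or omitted: 1/50 = 2 percentage points.
- Standard error of the difference, *assuming* the same recorded rate p in both arms, is sqrt(2 × p × (1 − p) / 50):
  - p = 5%: sqrt(0.0019) = 0.0436, or 4.4 points, about 4.36/2 = 2.2 patients.
  - p = 1%: sqrt(0.000396) = 0.0199, or 2.0 points, one patient.
  - p = 0.1%: sqrt(0.00003996) = 0.0063, or 0.6 points, 0.3 of a patient.

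Above a recorded rate of about 1%, a single decision is smaller than one standard error. Below that rate, fewer than one case is expected per arm. The SOC rate is an assumption, because the 8.4 figures describe the drug.

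**The case against.** The strongest reply is that little is left once the limits are stated. The exemption is conditional, it concerns a symptom of a minority of patients, AEs are asked about daily, and treated cases can appear in the medication tables. All of this stands and keeps the point minor. It does not close the gap, because the condition that ends the exemption is a judgement by the same person who knows the arm.

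A second reply is that the fix goes beyond the one symptom shown to overlap. That is fair as to the evidence. But the symptoms in 2.1 are given as examples, so other 8.4 symptoms could also be taken for COVID-19, and reusing an existing list is simpler than writing a rule for diarrhea alone.

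A reader might also infer stronger points that the documents do not support:

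- **Laboratory and vital-sign findings.** Section 8.1 also exempts "Any clinically significant abnormal laboratory findings or other abnormal safety assessments which are associated with the underlying disease", while 7.4.1, 7.4.2 and 8.3 make clinically significant findings AEs without that exception. The natural reading is that 8.1 defines the term and carves out disease-related findings, and that the other sections restate the general rule. A cross-reference is missing, but SAP 12.3 and 12.4 tabulate these data by arm whatever their AE status.
- **ALT/AST.** In 8.3, a change of ifenprodil dose is a trigger that SOC cannot meet. But judged clinical importance is an alternative trigger open to every arm, and 5.5 already speaks of liver-enzyme rises as adverse events for patients generally.
- **Hypotension and bleeding.** Their overlap with COVID-19 is only an inference from the severe complications in 2.1, and 5.5 already calls them adverse events.
- **Serious events.** Diarrhea that meets a seriousness criterion in 8.6.1 would ordinarily be more severe than expected, so the exemption would lapse under its own wording.

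**Conclusion.** The point holds in a narrow form. In Phase 2b, entry of diarrhea as an AE can depend on arm, because an investigator who knows the arm must first decide whether it is expected COVID-19, and no other rule requires its entry. This rests on 2.1 and 8.4 read together with 8.1, on the absence of any override, and on the absence of a scheduled measurement.

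It would go too far to say that the AE comparison is biased. No difference in recording is shown, and its direction and size cannot be derived. At an assumed 5% in both arms, one decision (2 points) lies within sampling error (4.4 points); several decisions in the same direction would not necessarily do so. Severity is minor: this is an inexpensive improvement in wording. The point applies to the open-label stage, since Phase 3 is planned as double-blind.

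**What to change.** Add one exception to the first disease-related bullet in the list of non-events in Protocol 8.1. The events of special interest listed in 8.4 are recorded as AEs in all three arms, whatever the presumed cause. Attribution is then made only in the causality field of 8.2.2.3, which already allows for events explained by an underlying condition. Other COVID-19 signs and symptoms stay exempt, and the bullet on laboratory and other safety findings is left as it is.

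The cost is a change to the protocol wording and the eCRF completion guidance, made through the amendment procedure in 11.1. No new assessments are needed. The downside is more AE entries in every arm, many of them caused by the disease. The change removes the attribution step before entry; it does not mask the recognition or reporting of symptoms, which stays open-label.

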#### **8.1.1 Treatment Emergent Adverse Events**

Treatment emergent adverse events (TEAE) are undesirable events do not present prior to medical treatment, or an already present event that worsens either in intensity or frequency following the treatment up to and including the follow up period.

## **8.2 Collection and Reporting of Adverse Events**

### **8.2.1 Collection of Treatment Emergent Adverse Events**

The Investigator must monitor the condition of the patient throughout the trial from signing the ICF until the last visit.

The sources of treatment emergent adverse events cover:

- The patient's response to questions about his/her health (a standard non-leading question such as "How have you been feeling since your last visit?" is asked at each visit).
- Symptoms spontaneously reported by the patient.

- Investigations and examinations where the findings are assessed by the Investigator to be clinically significant changes or abnormalities.
- Other information relating to the patient's health becoming known to the Investigator (e.g. hospitalisation).

When an TEAE/SAE occurs, it is the responsibility of the investigator to review all documentation (e.g., hospital progress notes, laboratory, and diagnostics reports) relative to the event. The investigator will then record all relevant information regarding an TEAE/SAE in the e-CRF. It is not acceptable for the investigator to send photocopies of the patient's medical records in lieu of completion of the TEAE/SAE e-CRF page.

## **8.2.2 Reporting of Treatment Emergent Adverse Events**

A qualified Investigator will evaluate all TEAEs as to:

### **8.2.2.1 Adverse Event**

- Adverse events should be recorded as diagnoses, if available. If not, separate signs and symptoms should be recorded. One diagnosis/symptom should be entered per record.
- If a patient suffers from the same adverse event more than once and the patient recovers in between the events, the adverse events should be recorded separately.
- Note the following: A procedure is not an adverse event; the reason for conducting the procedure is. Hospitalisation is not an adverse event; the reason for hospitalisation is. Death is not an adverse event, but the cause of death is (an exception is sudden death of unknown cause, which is an adverse event).

### **8.2.2.2 Intensity**

For both AEs and SAEs, the Investigator must assess the severity/intensity of the event and assign to one of the following categories ([NCI CTCAE](#)):

#### ***Mild***

- Asymptomatic or mild symptoms; clinical or diagnostic observations only
- Everyday activities minimally or not affected
- Intervention not indicated; no or minimal therapy required

#### ***Moderate***

- Symptom(s) cause moderate discomfort
- Some interference with normal everyday activities
- Local or non-invasive intervention indicated; drug therapy may be required

#### ***Severe***

- Symptoms causing severe discomfort/pain
- Inability to perform daily social and functional activities (e.g. absenteeism and/or bed rest)
- Symptoms requiring medical/surgical attention/intervention; drug therapy is required

- An event is categorized as “serious” when it meets one of the pre-defined criteria for seriousness; an event may be severe in intensity but be of relatively minor medical importance (e.g. a severe headache). An event that is categorized as severe will not be confused with an SAE.

***Life Threatening***

- Life threatening consequences
- Urgent intervention required

***Death***

**8.2.2.3 Causality**

The possibility of whether the IP caused the adverse event must be classified as one of the following:

***Reasonable possibility***

The term “reasonable possibility” conveys that there is evidence or argument to suggest a causal relationship between the IP and the adverse event, rather than to imply that a relationship cannot be ruled out. The adverse event may occur as part of the pharmacological action of the IP or may be unpredictable in its occurrence

***No reasonable possibility***

A causal relationship of the AE to IP administration is unlikely or remote, or other medications, therapeutic interventions, or underlying conditions provide a sufficient explanation for the observed event

Causality should be assessed and provided for every AE/SAE based on currently available information. Causality is to be reassessed as necessary and provided as additional information becomes available.

**8.2.2.4 Duration**

The investigator will record the start and stop dates of the event. The date of onset is the date when the first sign(s) or symptom(s) were first noted. If the adverse event is an abnormal clinically significant laboratory test or outcome of an examination, the onset date is the date the sample was taken, or the examination was performed. For pre-existing clinically significant conditions (diagnosed or observed as a result of the screening procedures) becoming worse after IP administration, the date of onset is the date the worsening began. The date of outcome is the date the patient recovered or died, or that the disease condition worsened.

